The present study was conducted over a period of 14 days with the aim of observing the effects of white tea consumption on anthropometric parameters, blood pressure, haematology, biochemistry, and antioxidant enzymes activity. Prior to the intervention, subjects were instructed to undergo a washout phase. During the washout phase, subjects were instructed to refrain from consuming vitamins, herbal drinks containing spices (turmeric, ginger, and galangal), fruits with high flavonoid content (grapes, apples, oranges, and their processed products), and products containing high levels of tannins (coffee, other types of tea, and chocolate). This approach was adopted to mitigate potential bias and to avert the occurrence of anemia or other forms of toxicity.

Subsequently, a series of anthropometric, blood pressure, complete haematology, and biochemistry tests are conducted to ascertain which subjects meet the criteria to proceed to the research stage. Subjects who meet the specified criteria will then be educated on the art of tea-making and instructed to consume it for a period of 14 days. During the administration stage of white tea, subjects are instructed to refrain from using the products that they abstained from during the washout stage. Anthropometric measurements, blood pressure, complete haematology, and biochemistry tests will be performed again on day 15 and the day after last day white tea administration. Subsequently, all subjects will undergo a period of post-intervention monitoring (the observation phase) for a duration of seven days. The purpose of this monitoring is to ensure that no deleterious effects result from the white tea intervention.

Sample Size Calculation

This study is a pilot study, and the minimum sample size calculation will be performed using the thumb method through an NCT approach with 90% power and a significance value of 5%. The calculation indicated that, given a 20% attrition rate, a sample size of 19 subjects was required for the study.

Subject:

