All data pertaining to the study will be stored on CRFs/individual screening sheets. The data will be recorded in both soft and hard file formats on a daily basis.

Evaluation Criteria

Anthropometric measurements, blood pressure, haematology, and biochemistry tests will be conducted before the intervention and one day after the last intervention (day 0 and day 15). Anthropometric measurements, blood pressure, and blood sampling will be conducted at the Faculty of Pharmacy, Padjadjaran University. The biochemical examinations will be carried out at the clinical laboratory of the Bandung City Health Office, while the complete haematology and antioxidant enzyme examinations will be carried out at the Biomedical Laboratory of the Faculty of Medicine, Padjadjaran University. The results of the examinations conducted before and after the white tea intervention will be analyzed to ascertain the effect of white tea consumption over a period of 14 days. The types of food and beverages consumed by the research subjects and their daily activities were recorded in the CRF for a period of 28 days (from the wash-out phase to the observational phase).

Statistical Analysis

The effect of white tea administration will be compared before and after treatment using a t-test analysis.

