This study will analyze the potential effects of consuming white tea for 14 consecutive days. During the 7 days prior to white tea consumption (wash-out stage) and the 14 days during white tea consumption (treatment stage), all research subjects were instructed to avoid consuming products high in flavonoids, such as vitamins, herbal drinks containing spices (turmeric, ginger and kencur), fruits high in flavonoids (grapes, apples, oranges and their processed products), and products containing high levels of tannins (coffee, other types of tea, and chocolate). This was done to avoid excessive flavonoid intake, which can trigger anaemia and the formation of pro-oxidants. In addition, the presence of other strong antioxidants can also cause errors in the test (leading to bias) due to the influence of other antioxidant products. Furthermore, all respondents will be asked to drink white tea (made by brewing 4 grams of white tea in 200 mL of hot water) every morning one hour before eating or two hours after eating. To ensure the compliance of the research subjects, we will ask respondents to send videos of themselves consuming white tea, monitor and record the food and drinks consumed by all subjects in the CRF.

White tea is a type of tea that is believed to have better antioxidant content than other types of tea due to its high content of flavonoid compounds, especially catechins. If regular consumption of white tea for 14 days is proven to have a positive effect on anthropometric parameters, lipid profile, blood sugar levels and increases antioxidant enzyme activity, and is proven to be safe when reviewed from haematological parameters, ALT, AST, serum creatinine levels and eGFR, then this product can be further developed as a product for adjuvant therapy in various types of diseases. This study was conducted as an initial test of the potential of white tea for health before further exploration for application to a specific disease.

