6. TARGET POPULATION AND SAMPLE SIZE

The population utilised in this study comprised healthy subjects residing at Padjadjaran University and its environs who had completed the recruitment form on Google Forms. The respondents' data that had been entered underwent preliminary screening based on the following inclusion and exclusion criteria.

Inclusion criteria

- a. Participants are members of the Padjadjaran University community and surrounding areas aged 20-35 years (excluding women who were either unmarried or sexually inactive).
- b. Participants must not have been smokers for less than 5 years.
- c. Participants must not have a history of anaemia, liver or kidney disease.

Exclusion criteria

- a. Participants were required to take certain medications or vitamin supplements.
- b. The subjects reported experiencing discomfort during the administration of the product.
- c. Prior to the initiation of treatment, biochemical results were found to be outside the normal range.

This study utilised a pilot study, and the minimum sample size calculation was performed using the thumb method with a non-central t-distribution (NCT) approach. Whitehead stated that the minimum sample size for a power (β) value of 90% and a significance (α) value of 5% is 15 for each group. Considering a 20% possibility of dropouts, we used 19 subjects in the study. The following table provides a reference for the calculation of the sample size, as outlined by Whitehead et al. (2016) (27).

Table 8. Estimated stepped rules of thumb for required pilot trial sample size per treatment arm when the NCT approach will be used to calculate the main trial sample size.

Standardised difference	80% powered main trial	90% powered main trial
Extra small ($\delta < 0.1$)	50	75
Small ($0.1 \leq \delta < 0.3$)	20	25
Medium ($0.3 \leq \delta < 0.7$)	10	15
Large ($\delta \geq 0.7$)	10	10

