8. STATISTICAL ANALYSIS

The mean data before and after treatment will be tested for homogeneity and normality. In order to draw parallels between the two data sets, parametric measurements will be considered using the T-test for data with normal distribution, while data with abnormal distribution will be analyzed using a non-parametric test, namely the Wilcoxon test. The statistical analysis of all data will be conducted using SPSS version 20.0.

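### The 90% power stated for this study belongs, in the protocol's own table, to a later main trial; it is unsupported for this one-group before/after design.

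*Combined protocol and SAP*

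**What the plan says.** Section 1.1 (Sample Size Calculation) says the minimum size comes from "the thumb method through an NCT approach with 90% power and a significance value of 5" per cent, and that 19 subjects are needed after 20% attrition. Section 6 attributes the figure to a published rule: "the minimum sample size for a power (β) value of 90% and a significance (α) value of 5% is 15 for each group". It then raises 15 to 19 for dropout.

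Section 6 also reproduces the source table. Its caption describes the "required pilot trial sample size per treatment arm when the NCT approach will be used to calculate the main trial sample size". The column that contains 15 is headed "90% powered main trial".

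The design in Sections 1.1 and 4 is a pilot with one group measured before and after 14 days of tea. On the analysis, Section 1.1 says: "The effect of white tea administration will be compared before and after treatment using a t-test analysis". Section 8 adds that "parametric measurements will be considered using the T-test for data with normal distribution", with a Wilcoxon test otherwise. Neither section says whether the t-test is paired or whether it is one- or two-sided.

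**The concern.** Sections 1.1 and 6 attach 90% power at 5% significance to this study's sample size, while the table cited for it attaches 90% to a different, later trial. Under its caption, the table shows how large a pilot arm should be when its results will be used to size that trial. It does not show that a pilot of 15 has 90% power for anything. It is also expressed per treatment arm, has no significance level in it, and is used here for a single group.

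This matters because 90% is the only power figure offered in support of 19 subjects, and Section 1.2 gives the results some weight. If effects are shown and the tea "is proven to be safe when reviewed from haematological parameters, ALT, AST, serum creatinine levels and eGFR, then this product can be further developed", development is to continue. A reader who takes 90% at face value may find a non-significant change in ALT, creatinine or haemoglobin more reassuring than it is. The documents set no rule for interpreting a non-significant result, so this is a risk of misreading and not a planned error.

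**Working it through.** **Inputs from the documents**
- Power 90%, significance 5% (Sections 1.1 and 6); sidedness not stated.
- Pilot size 15, dropout 20%, final size 19 (Section 6).
- One group, before/after t-test or Wilcoxon test (Sections 1.1, 4 and 8).
- Not given for the calculation: primary endpoint, target change, SD of the change, pre/post correlation.

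**Step 1: reproduce 19.** 15/(1 − 0.20) = 18.75, rounded up to 19. This agrees with the plan.

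**Step 2: trace 15.** It occurs in one cell only: the medium row (0.3 ≤ δ < 0.7) of the 90% main-trial column. The text neither names nor justifies that row.

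**Step 3: power of this study's own test (illustration).** Assume a paired t-test and let d = mean change / SD of the change. With n completers, the test statistic follows a noncentral t distribution with n − 1 degrees of freedom and noncentrality d√n. Two-sided power is the probability that it falls outside ±t(0.975, n − 1). For n = 15 and d = 0.5, the noncentrality is 0.5 × √15 = 1.94 and power is 0.438.

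| Test | n | d = 0.3 | d = 0.5 | d = 0.7 | d for 90% power |
|---|---|---|---|---|---|
| Two-sided 5% | 15 | 19% | 44% | 71% | 0.90 |
| Two-sided 5% | 19 | 24% | 54% | 82% | 0.79 |
| One-sided 5% | 15 | 30% | 58% | 82% | 0.80 |

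On this scale, no effect in the medium row reaches 90% with 15 completers, whether the test is one- or two-sided.

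**Step 4: the same check on the between-subject scale.** The table is per arm, so its δ may be in between-subject SDs. With equal SDs before and after and correlation r, d = δ/√(2(1 − r)). The δ detectable with 90% power is 0.901 × √(2(1 − r)). The documents do not give r, so a range is assumed (n = 15, two-sided):

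| r | d when δ = 0.5 | Power at δ = 0.5 | δ for 90% power |
|---|---|---|---|
| 0.3 | 0.423 | 33% | 1.07 |
| 0.5 | 0.500 | 44% | 0.90 |
| 0.7 | 0.645 | 64% | 0.70 |
| 0.8 | 0.791 | 81% | 0.57 |
| 0.9 | 1.118 | 98% | 0.40 |

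At the top edge of the row (δ = 0.7), r = 0.7 gives 90%.

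**Step 5: precision.** The 95% confidence interval for a mean change has half-width t(0.975, n − 1)/√n in SDs of the change: 0.55 with 15 completers and 0.48 with 19.

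**The case against.** The strongest reply is that the study is openly a pilot sized by a rule of thumb. Section 6 reports what the cited source states and prints the correctly labelled table directly below, so a careful reader can see where 15 comes from. That softens Section 6, but not Section 1.1, which attaches 90% power to this study's calculation with no table beside it. And if power does not matter for a pilot, the figure should go.

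A second reply is that the low powers in Step 3 depend on reading the table's 0.3 to 0.7 band in SDs of the within-subject change, which nothing establishes. This stands. Step 4 shows that highly correlated endpoints could reach 90%. One narrow case also exists on the Step 3 scale: a one-sided test with all 19 completing reaches 90% at 0.698, just inside the medium row. It needs a one-sided test that the plan does not specify and no dropout, against its own 20% allowance. These points limit the conclusion to unsupported; they do not supply the missing support.

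Third, the harm is conjectural: Section 1.2 also calls the study an initial test before further exploration, and nothing says the 90% will be used to interpret null results. That is fair, and it is why this is a correction of wording and reporting rather than a challenge to the design.

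**Conclusion.** The concern holds. The stated 90% is the power of a later main trial in the table the protocol reproduces, and nothing in the documents makes it a property of this study. The arithmetic from 15 to 19 is right; the error lies in what the 90% refers to.

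The size of the gap cannot be fixed without an endpoint. With 15 completers and a two-sided 5% paired t-test, power across the band from 0.3 to 0.7 SDs of the change is 19% to 71%. For a change of 0.5 between-subject SDs it is 33% to 98% as r goes from 0.3 to 0.9. Pairing, two-sidedness, equal SDs and r are assumptions. The figures also apply to one test at 5%, with no primary endpoint named and no adjustment for multiple parameters, and to the t-test rather than the Wilcoxon alternative. This should be fixed, but it does not undermine the choice of 19 subjects for a pilot.

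**What to change.** Keep 19 subjects. In Sections 1.1 and 6, remove 90% as the power of this study and state what the table supports, for example: *Fifteen is a rule-of-thumb pilot size per treatment arm for a medium standardised difference; the 90% refers to a future main trial. Allowing for 20% dropout gives 19.* Give a reason for choosing the medium row.

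If a power statement is wanted, label its assumptions: *Assuming a two-sided 5% paired t-test, 15 completers give 90% power for a mean change of about 0.90 SD of the change or larger.* Otherwise omit it.

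In Section 8, add that each mean change will be reported with its 95% confidence interval and the SD of the change, which is what planning a main trial requires. Add that a non-significant result will not by itself be read as no effect or no harm, but judged from the interval.

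The cost is a few sentences in Sections 1.1 and 6 and a short reporting addition in Section 8. There are no extra subjects, visits or tests. The one drawback is that the power statement becomes less favourable.

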7. RESEARCH PROCEDURE

7.1. Recruitment of Respondents and Initial Screening

The data collected from respondents will undergo a review and selection process, with this being based on predetermined inclusion and exclusion criteria. A proportion of respondents who meet the specified criteria will be directed to undergo a 7-day washout period. The purpose of this procedure is to prevent bias in the initial screening process. During this phase, subjects are instructed to avoid the consumption of vitamins, herbal drinks containing spices (turmeric, ginger and galangal), fruits with high flavonoid content (grapes, apples, oranges and their processed products), and products containing high levels of tannins (coffee, other types of tea, and chocolate).

7.2. Procedures for Requesting Permission from Research Subjects

Patients who are deemed to be eligible will be provided with an explanation of the research process and will be requested to provide their voluntary consent. As the population under study consists of adults in good health, consent must be obtained directly from the participant via a process of signing the consent form after receiving an

explanation (informed consent). The signing process will be initiated subsequent to the subject being deemed to have comprehended the explanation pertaining to the research. The signing process will be carried out by the respondent, the researcher, and a witness who will observe the consent process.

7.3. Respondents Selection

Patients who have been declared eligible during the preliminary screening and have signed the consent form will be provided with instructions on how to prepare the tea. It is imperative that the CRF be completed in a manner that is both legible and exhaustive.

7.4. Provision of Test Products

Following the endorsement of the consent form, each subject will be furnished with a set of fourteen tea bags, each containing four grams of white tea. These tea bags will be accompanied by comprehensive instructions detailing the optimal preparation of the tea. Subjects are instructed to brew one tea bag in hot water for 10 minutes. The tea must be consumed one to two hours after breakfast for a period of 14 days.

Product Storage

White tea products should be stored in a sealed container at room temperature.

Guarantee of research subject compliance

Subject compliance will be monitored each morning by asking subjects to send a video of themselves drinking the beverage product every day.

7.5. Respondent Monitoring

Monitoring of anthropometry and blood pressure

The subjects of the research will undergo physical monitoring, including weight, height, BMI, waist circumference and blood pressure, by research team on days 0 and 15 (one day before and one day after the last day of the white tea intervention).

Laboratory monitoring

Laboratory monitoring was conducted on days 0 and 15 (one day before and one day after the last day of the white tea intervention) on blood samples from subjects in order to determine the effects of drinking tea for a period of 14 days. Should the preliminary investigative results pertaining to haematological parameters (RBC, HB, HCT, MCV and MCH), ALT, AST, serum creatinine levels, eLFG and urea nitrogen levels demonstrate abnormality, the subject will be withdrawn from the study for reasons of safety. Haematological tests are performed to ensure that the subject is not anaemic. ALT and AST tests are performed to ensure that there is no liver dysfunction, while serum creatinine, eGFR, and urea nitrogen tests are performed to ensure that the subjects do not have kidney dysfunction. In summary, the parameters employed in this study to observe the effects of white tea consumption are outlined as follows:

- a. Hematology profile
- b. Lipid profil
- c. Fasting blood glucose
- d. ALT dan AST
- e. Serum creatinine level, urea nitrogen level and eGFR
- f. First line antioxidant enzymes (SOD, CAT dan GPx).

Monitoring consumption and daily activities

In order to ensure that respondents adhere to the prescribed dietary regime, researchers will ensure that subjects abstain from the consumption of particular products that must be avoided during the course of the research process. Researchers will record all food and beverages consumed, the subjects' daily activities, and any complaints that may be experienced by the subjects, whether related or unrelated to the administration of white tea products.

7.6. Discontinuation of Respondent Involvement in Research

Research subjects may withdraw from participation in the study, and researchers may also terminate a subject's involvement in the study if there is a deviation from the protocol. If a research subject is terminated for medical reasons, the researcher will ensure that their health is monitored until their condition improves.

7.7. Anthropometric Measurement

Measurements of body weight, height, and waist circumference for the study will be taken on day 0 (one day before the intervention) and day 15 (one day after the last day of the white tea intervention). Participants are advised to wear light clothing and remove their shoes before weight and height measurements. BMI values will be calculated using an online BMI calculator based on weight (kg) and height (cm) (nhlbi.nih.gov/health/education/lose_wt/BMI/bmi-m.htm).

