3.2. Research objectives

The objectives of this study are:

1. Determine the effect of white tea consumption on the anthropometry of healthy subjects based on body weight, body mass index (BMI), waist circumference, and blood pressure.
2. Determine the effect of white tea consumption on biochemical parameters in healthy subjects based on blood sugar levels, complete lipid profile (total cholesterol, low-density lipoprotein, high-density lipoprotein, and triglycerides), liver function activity (based on liver enzyme function including alanine aminotransferase and aspartate aminotransferase), and kidney function (through measurement of creatinine levels, estimated glomerular filtration rate, and urea nitrogen levels).
3. Determine the effect of white tea consumption on hematology profile parameters associated with anaemia, including total red blood cell count, haemoglobin, haematocrit, mean corpuscular haemoglobin (MCH), and mean corpuscular volume (MCV).
4. Determine the effect of white tea consumption on the first line antioxidant enzymes activity of healthy subjects, such as superoxide dismutase, catalase, and glutathione peroxidase.

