APPENDIX 1. SCREENING FORM FOR SUBJECTS

SAMPLE

Research Number:	Respondent's initials: [] [] []
------------------	------------------------------------

SCREENING 1 – PERSONAL DATA

PERSONAL DATA		Officer ()
Date of data collection	: [] / [] / [] (DD/MM/YY)	
Name / initial	: [] [] []	
Place and Date of Birth		
Age	: Tahun	
Gender	: Pria / Wanita *	
Job	:	
Address	:	
Contact	:	

Note: The first two boxes in the initials are filled in with the first two letters of the two words of the name, and the third box is filled in with the date of birth. If the date of birth contains two numbers, use only one of them.

Example: Name: [name], Date of Birth: Januari 8th → [L|C|8].

MEDICAL HISTORY

History	Yes	No	Unknown
Have you ever had anaemia within the last 5 years?			
Do you have a history of kidney disorder?			
Do you have a history of stomach ulcers or GERD?			
Do you have a history of liver disorder?			
Are you an active smoker < 5 years?			
Are there any family members who smoke?			
Are you undergoing any medical treatment? Please specify!			

Signature of officer after filling out form:

Initials:

Date:

SAMPEL

Research Number:	Respondent's initials: []
------------------	---

SCREENING 2 – ANTHROPOMETRY AND BLOOD PRESSURE

ANTHROPOMETRIC EXAMINATION (PRE)	
Body weight : kg	Body height : cm
BMI : kg/m ²	
Waist Circumference: cm	
BLOOD PRESSURE MEASUREMENT (PRE)	
Blood pressure:	

ANTHROPOMETRIC EXAMINATION (POST)	
Body weight : kg	Body height : cm
BMI : kg/m ²	
Waist Circumference: cm	
BLOOD PRESSURE MEASUREMENT (POST)	
Blood pressure:	

Signature of officer after filling out form: Initials: Date:

SAMPEL

Research Number:	Respondent's initials: []
------------------	----------------------------

SCREENING 3 – BLOOD AND BIOCHEMICAL TESTS

a. Initial Screening

Parameters	Test Date/Time	Result	Status
Hematology Profile	[] / [] / [] (DD/MM/YY) [] . [] WIB	RBC : $10^6/\mu\text{L}$ HB : g/dL HCT : % MCV : fL MCH : pg	 Eligible  Not Eligible
Lipid Profile	[] / [] / [] (DD/MM/YY) [] . [] WIB	TC : mmol/L HDL : mmol/L LDL : mmol/L Tg : mmol/L	 Eligible  Not Eligible
Fasting Blood Glucose	[] / [] / [] (DD/MM/YY) [] . [] WIB	mmol/L	 Eligible  Not Eligible
ALT	[] / [] / [] (DD/MM/YY) [] . [] WIB	$\mu\text{kat/L}$	 Eligible  Not Eligible

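### Measuring height again at day 15 puts height-measurement error into the BMI change; calculate both BMI values from one height per subject

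*Combined protocol and SAP*

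**What the plan says.** Section 7.7 sets the measurement times: "Measurements of body weight, height, and waist circumference for the study will be taken on day 0 (one day before the intervention) and day 15". Section 7.5 lists height and BMI together at both visits: "physical monitoring, including weight, height, BMI, waist circumference and blood pressure, by research team on days 0 and 15".

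BMI is derived as follows: "BMI values will be calculated using an online BMI calculator based on weight (kg) and height (cm"). The sentence does not say which visit's height is entered. In Appendix 1, Screening 2, the block headed "ANTHROPOMETRIC EXAMINATION (POST") has its own body-height field beside its own BMI field, like the pre-treatment block. No text carries the day-0 height forward.

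The only stated condition for measuring height is this: "Participants are advised to wear light clothing and remove their shoes before weight and height measurements". No device, replicate, rounding or same-observer rule is given. Blood pressure, by contrast, has a six-step procedure with three readings (section 7.8).

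Objective 1 in section 3.2 is assessed "based on body weight, body mass index (BMI), waist circumference, and blood pressure". Section 1.1 gives the comparison: "The effect of white tea administration will be compared before and after treatment using a t-test analysis". Section 8 adds the Wilcoxon test for non-normal data.

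**The concern.** Section 6 restricts enrolment by age: "Participants are members of the Padjadjaran University community and surrounding areas aged 20-35 years". True height at that age is constant over the 15 days between measurements. Any recorded difference is therefore error from posture, observer, time of day or rounding. BMI divides by height squared, so that error passes directly into the BMI change.

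With one height per subject, BMI change is weight change divided by a constant, and the two outcomes must agree in direction for every subject. With two heights they need not agree. A subject whose weight is unchanged can show a BMI change, and the BMI test can miss a change that the body-weight test detects. With 15 to 19 evaluable subjects, a few discrepant readings could leave the report with two results for the same objective that do not match. The cause would be the second height reading, not the tea.

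**Working it through.** **Figures in the plan.** The documents give no height-error SD, no weight-change SD and no expected BMI change, so there is no BMI figure to reproduce. The stated sample size does reproduce (15/0.80 = 18.75, rounded up to 19) and is not affected by this point.

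**Inputs.** From the documents: height at days 0 and 15, BMI from weight and height, age 20-35, pre-post comparison. Assumed: weight W = 63 kg; height H = 165 cm (1.65 m); independent height error with SD s_h = 0.5 cm per visit (range 0.3-0.7); SD of weight change s_w = 1.0 kg (range 0.7-1.5).

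**Step 1: effect of one misread height.** BMI = 63/1.65² = 23.14. With height read 1 cm too high, BMI = 63/1.66² = 22.86. The difference is 0.28 kg/m², and 0.278 × 1.65² = 0.76 kg of apparent weight loss.

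**Step 2: height part of the SD of BMI change.** By the delta method, the sensitivity is 2 × BMI/H = 2 × 23.14/165 = 0.2805 kg/m² per cm. Two independent readings give 0.2805 × 0.5 × √2 = 0.198 kg/m².

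**Step 3: weight part.** s_w/H² = 1.0/1.65² = 0.367 kg/m².

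**Step 4: combine.** √(0.367² + 0.198²)/0.367 = 1.14, so the SD rises by about 14%. Relative information is 1/1.136² = 0.77, a loss of about 23%.

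**Step 5: range.** The ratio of height variance to weight variance is 2 × (2W/H)² × (s_h/s_w)² = 2 × (0.7636)² × (s_h/s_w)² = 1.166 × (s_h/s_w)². Each cell shows SD inflation, then information loss:

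| s_h (cm) | s_w = 0.7 kg | s_w = 1.0 kg | s_w = 1.5 kg |
|---|---|---|---|
| 0.3 | 10%, 18% | 5%, 9% | 2%, 4% |
| 0.5 | 26%, 37% | 14%, 23% | 6%, 11% |
| 0.7 | 47%, 54% | 25%, 36% | 12%, 20% |

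**Step 6: the same in terms of power.** At a second set of assumed values (60 kg, 160 cm, s_w = 0.8 kg), take a BMI change that a paired two-sided 5% test would detect with 80% power using one height. With height re-measured, power is 77%, 74%, 65% and 39% for s_h = 0.2, 0.3, 0.5 and 1.0 cm. The result is the same for n = 15 and n = 19. A simulation of 1,000,000 draws at s_h = 0.5 cm gave an SD of BMI change of 0.375 with two heights and 0.312 with one, which agrees with the formula.

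**Step 7: what remains with one height.** Error in the single reading only rescales the change. A 0.5 cm error alters a subject's BMI change by a factor of about 2 × 0.5/165 = 0.6%, which is negligible.

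**The case against.** The strongest objection is that little is lost at trial level. Body weight is a separate outcome under the same objective and carries no height error. With one fixed height, BMI change is only weight change rescaled for each subject. The information lost is therefore lost from a near-duplicate outcome, and BMI is one of many outcomes with none named primary. This stands, and it is why the point is minor.

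A reader might infer that re-measuring height could create a BMI effect where there is none. For the group result, the documents do not support that. Independent error at the two visits does not shift the mean change. It widens the SD of the differences, and a paired t-test carries that into its standard error, so the false-positive rate does not rise. A false mean change would need a systematic difference between visits in observer, device or time of day. The plan does not rule this out, but nothing in it shows that it will happen. For a single subject, a false change can occur (step 1).

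It can also be said that no single sentence states that day-15 BMI uses day-15 height. That is correct; it is an inference. It remains the natural reading, because height and BMI are listed together at both visits, the form pairs them, and no other rule is given.

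Finally, the size depends on assumed SDs. At s_h = 0.2 cm and s_w = 1.0 kg the SD inflation is only about 2%. The plan does not require the careful height measurement that would secure so small an error. The direction of the effect does not depend on the assumptions.

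**Conclusion.** The point holds as a small, avoidable loss of precision in one named outcome. As written, the plan most naturally adds height-measurement noise to the BMI change of adults whose height is fixed. The central estimate is 14% SD inflation (23% information loss), and the range is about 2-47% (4-54%). All of these figures rest on the assumed weight, height and SDs, and on independent errors at the two visits. The effect is confined to BMI: body weight, waist circumference and blood pressure do not use height. It would not change the trial's overall conclusions, but it could leave BMI and weight results that appear to conflict within objective 1.

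**What to change.** Add one sentence to section 7.7: BMI at both visits is calculated from a single height per subject, either the day-0 height or the mean of the two readings, with the choice fixed in advance. In Appendix 1, Screening 2, remove the post-treatment height field, or keep it and label it as a quality check that does not enter the BMI calculation. It would also help to note in section 8 that BMI change is then body-weight change rescaled by each subject's height, so that the two results are not read as independent evidence.

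This needs no extra subjects, visits or measurements. If the study is already under way, the change goes to the Ethics Committee as a protocol amendment under section 14. For data already collected, BMI can be recalculated from the recorded weights and heights.
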